APPENDIX D. PROTOCOL AMENDMENT SUMMARY OF CHANGES

Document	Date
Amendment 1	10 SEP 2021

Amendment 1 (10 SEP 2021)

Overall Rationale for the Amendment:

The primary purpose of the amendment is to obtain additional long-term safety and efficacy data through 104 weeks; and to incorporate changes from country-specific amendments for Germany (dated 04 DEC 2020) and Canada (dated 08 MAR 2021). Additional changes are summarized below.

 Section 1, Protocol Summary (Table 2: Key Study Design Elements; Table 3: Schedule of Activities); Section 2.1.2, Scientific Rationale for Study Design; Section 2.1.3, Justification of Dose; Section 2.2.2, Benefit Assessment; Section 3, Objectives and Endpoints (Table 5: Objectives and Endpoints); Section 4.1, Overall Design; Section 4.2, Overall Study Duration; Section 6.1, Study Treatments Administered (Table 6: Study Treatment Information); Section 6.3, Measures to Minimize Bias: Randomization and Blinding; Section 6.5.1, Criteria and Procedures for Dose Interruptions and Adjustments of Study Drug; Section 6.6.2, Restricted Medication and Procedures; Section 6.6.4.2, Number of Rescue Interventions; Section 6.7, Treatment After the End of the Study; Section 7.1.2, Discontinuation Procedures; Section 7.2, Participant Withdrawal From the Study; Section 8.7, End of Treatment and/or Early Termination

Description of change: At the completion of the 36-week OLE period (preceded by the 16-week placebo-controlled period), all eligible participants will have the option to continue treatment for an additional 48 weeks (LTE period), followed by a 4-week safety follow-up period.

Rationale for change: To obtain additional long-term safety and efficacy data through 104 weeks.

4. Section 2.1.4, Justification for Placebo

Description of change: Added Section 2.1.4, Justification for Placebo.

Rationale for change: Per request made by the Germany's Health Authority to provide a rationale for a placebo arm in this HS study.

5. Section 2.1.5, Justification for Doses in the Long-term Extension

Description of change: Added Section 2.1.5, Justification for Doses in the Long-term Extension.

Rationale for change: To provide a rationale for the long-term extension and the doses available in that period.

6. Section 5.1, Inclusion Criteria

Description of change: Added Inclusion Criterion 6.

Rationale for change: Per request made by the Germany's Health Authority to determine that participants must have been previously exposed to at least 1 line of HS treatment (systemic antibiotics) before starting this study.

7. Section 6.5.1, Criteria and Procedures for Dose Interruptions and Adjustments of Study Drug (Table 7: Guidelines for Interruption, Restart, and Discontinuation of Study Drug)

Description of change: Added clarification on the guidance for study drug interruption/restart when AST and/or $ALT > 3.0 \times ULN$.

Rationale for change: To clarify that Appendix C should be consulted and to specify that the study drug can only be interrupted/restarted up to 2 times.

8. Section 6.5.1, Criteria and Procedures for Dose Interruptions and Adjustments of Study Drug (Table 7: Guidelines for Interrupting, Restarting, and Discontinuing Study Drug)

Description of change: Revised sentences that explained study treatment reinitiation after study treatment is interrupted when a platelet count between $50 \times 10^9/L$ to $< 75 \times 10^9/L$ is observed.

Rationale for chance: Per request made by Health Canada to provide a clarification that study treatment in the open-label extension will be reinitiated when platelet count is $\geq 100 \times 10^9/L$.

9. Section 8.3.7, Laboratory Assessments (Table 10: Required Laboratory Analytes)

Description of change: Creatine kinase was added to the list of analytes in the chemistry column.

Rationale for change: To align with emerging literature suggesting that JAK inhibitors may lead to increases in creatine kinase.

10. Section 8.3.7, Laboratory Assessments (Table 10: Required Laboratory Analytes)

Description of change: Erythrocyte sedimentation rate (ESR) was removed from the Inflammation Markers subheading.

Rationale for change: The inflammation markers assessment will focus on the high sensitivity C-reactive protein results, thus not requiring ESR evaluation.

11. Section 9.4, Reporting of Serious Adverse Events

Description of change: Added clarification for timing of SAE reporting.

Rationale for change: Per request made by the Germany's Health Authority to clarify that SAE reporting must happen immediately and not later than within 24 hours.

12. Appendix A, Information Regarding Effectiveness of Contraceptive Methods

Description of change: The following updates (deletions indicated by strikethroughs; insertions indicated by underlines) were made:

# LIST OF ABBREVIATIONS

Abbreviations	Definition
AE	adverse event
ALT	alanine aminotransferase
AN	abscess and inflammatory nodule
ANF	abscess, inflammatory nodule, and draining fistula
AST	aspartate aminotransferase
CTCAE	Common Terminology Criteria for Adverse Events
DILI	Drug Induced Liver Injury
DLQI	Dermatology Life Quality Index
DMC	data monitoring committee
ECG	electrocardiogram
eCRF	electronic case report form
HDL	high-density lipoprotein
HS	hidradenitis suppurativa
IHS4	International Hidradenitis Suppurativa Severity Score System
ITT	intent-to-treat
LDL	low-density lipoprotein
LTE	long-term extension
MedDRA	Medical Dictionary for Regulatory Activities
MMRM	mixed model repeated measures
NCI	National Cancer Institute
NRI	non-responder imputation
OLE	open-label extension
PC	placebo-controlled
DD	per protocol

РТ	preferred term	
QALYs	quality-adjusted life years	
QD	once daily	
QTcF	Fridericia's corrected QT interval	
SAP	Statistical Analysis Plan	
SOC	system organ class	
D.		
TEAE	treatment-emergent adverse event	
ULN	upper limit of normal	
	a	

## **1. INTRODUCTION**

This is a Phase 2, multicenter, parallel group, placebo-controlled, double-blind, randomized study to evaluate the efficacy and safety of INCB054707 (15, 45, and 75 mg QD) over a 16-week PC period. Upon completion of the 16-week PC period, participants will continue for 36 weeks of OLE period (INCB054707 75 mg QD). At the end of the OLE period, all eligible participants have the option to continue treatment for additional 48 weeks in an LTE period, to collect long-term safety and efficacy data for a total of 104 weeks. A safety follow-up visit will be conducted approximately 4 weeks after the last dose of study drug.

The purpose of this SAP is to provide details of the statistical analyses that have been outlined in the Study INCB 54707-204 Protocol.

## 2. STUDY INFORMATION, OBJECTIVES, AND ENDPOINTS

### 2.1. Protocol and Case Report Form Version

This SAP is based on INCB 054707-204 Protocol Amendment 1 dated 10 SEP 2021 and CRFs approved 27 JUL 2020. Unless superseded by an amendment, this SAP will be effective for all subsequent Protocol amendments and eCRF versions.

### 2.2. Study Objectives and Endpoints

Table 1 presents the objectives and endpoints.

#### Table 1:Objectives and Endpoints

Objectives	Endpoints	
Primary		
To determine the efficacy of INCB054707	• Mean change of AN count at Week 16 relative to baseline.	
Secondary		
To further evaluate the efficacy of INCB054707	• Key secondary endpoint: Proportion of participants who achieve HiSCR at Week 16. Hidradenitis suppurativa clinical response is defined as at least a 50% decrease from baseline in AN count with no increase in the number of abscesses or draining fistulas.	
	• Proportion of participants who achieve HiSCR at each visit from Weeks 2 to 12.	
	• Proportion of participants who achieve at least a 75% decrease from baseline in AN count with no increase in the number of abscesses or draining fistulas from Weeks 2 to 16.	
	• Mean change from baseline in the severity of the disease, as assessed by the IHS4 score, from Weeks 2 to 16.	
	• Proportion of participants achieving AN50, AN75, AN90, and AN100 (at least 50%, 75%, 90%, and 100% reduction in AN count relative to baseline, respectively) from Weeks 2 to 16.	
	• Mean change in AN count at Weeks 2 to 12, relative to baseline.	
	• Proportion of participants with a total AN count of 0 to 2 from Weeks 2 to 16.	
	• Mean change in draining fistula count from Weeks 2 to 16, relative to baseline.	
	• Mean change in ANF count from Weeks 2 to 16, relative to baseline.	

Objectives	Endpoints
To evaluate the safety and tolerability of INCB054707	• Frequency and severity of AEs, including the evaluation of clinical laboratory results, vital signs, ECGs, and the results of physical examinations.

Objectives	Endpoints

Objectives	Endpoints

## **3. STUDY DESIGN**

This is a Phase 2, multicenter, randomized, parallel group, placebo-controlled, dose-ranging study to evaluate the efficacy and safety of INCB054707 (15, 45, and 75 mg QD) over a 16-week PC period followed by a 36-week OLE period (INCB054707 75 mg QD) and an additional optional 48-week LTE period. The study will enroll men or women aged 18 to 75 years who have been diagnosed with HS (Hurley Stage I, II, or III) for at least 3 months with a total AN count of at least 5 and inflammatory lesions that affect at least 2 distinct anatomical areas.

Participants will undergo screening within 30 days prior to randomization. Participants who continue to meet eligibility criteria at baseline will have Day 1 (Week 0) assessments and will be randomized to 1 of 4 treatment groups. Participants will be stratified based on geographical region (North America and outside of North America) and disease severity (Hurley Stages I, II, and III) with no more than 25% of the total number of participants as Hurley Stage III.

Participants will receive double-blinded study treatment of placebo or 1 of 3 doses of INCB054707 (15, 45, or 75 mg) QD for 16 weeks. At Week 16, participants will enter the 36-week OLE period (INCB054707 75 mg QD). At the completion of the OLE period, all eligible participants will have the option to continue treatment for an additional 48-week LTE period. A safety follow-up visit will be scheduled approximately 4 weeks after the end of OLE period (Week 56 visit) for participants who do not continue into the LTE period, or the LTE period (Week 104 visit) for participants who continue into the LTE period.

The study schema is shown below in Figure 1.

#### Figure 1: Study Design Schema

The primary analysis will occur after the primary database lock, when all participants have completed or discontinued from the placebo-controlled, double-blind treatment period.

The final analysis will occur when all participants have completed or withdrew from the study.

## **3.1.** Randomization

Approximately 200 participants will be randomized 1:1:1:1 to 1 of 3 INCB054707 treatment groups or the placebo group (approximately 50 participants per group).

Participant randomization will be stratified based on geographical region (North America and outside of North America) and disease severity (Hurley Stages I, II, and III) with no more than 25% of the total number of participants as Hurley Stage III.

## **3.4.** Schedule of Assessments

Refer to Protocol Amendment 1 dated 10 SEP 2021 for a full description of all study procedures and assessment schedules for this study.

## 4. DATA HANDLING DEFINITIONS AND CONVENTIONS

### 4.1. Scheduled Study Evaluations and Study Periods

#### 4.1.1. Day 1

Day 1 is defined in Table 2 for each period, and combination of periods specified. Note that the treatment groups for each period are described in Section 5.2.

Treatment Period	Treatment Groups	Day 1
PC period	Placebo INCB054707 15 mg INCB054707 45 mg INCB054707 75 mg	The day of the first dose of study drug (INCB054707 or placebo) administered to the participants in the PC period.
OLE period	Placebo to INCB054707 75 mg INCB054707 15 mg to 75 mg INCB054707 45 mg to 75 mg INCB054707 75 mg	The day of the first dose of study drug (INCB054707 75 mg) administered to the participants in the OLE period
Throughout study participation up to Week 52	INCB054707 75 mg	The day of the first dose of study drug (INCB054707 75 mg) administered to the participants in the PC period
LTE period	INCB054707 ≤ 45 mg INCB054707 ≥ 60 mg	The day of the first dose of study drug (INCB054707) administered to the participants in the LTE period

Table 2:Definition of Day 1

For randomized participants not treated with any study drug, Day 1 is defined as the day of randomization.

#### 4.1.2. Study Day

If a visit/reporting date is on or after Day 1, then the study day at the visit/reporting date will be calculated as

Day # = (visit/reporting date - Day 1 date + 1).

If the visit/reporting date is before Day 1, then the study day at the visit/reporting date will be calculated as

Day # = (visit/reporting date - Day 1 date).

A study day of -1 indicates 1 day before Day 1.

#### 4.1.3. Baseline Value

Baseline is the last nonmissing measurement obtained before the first administration of INCB054707 or placebo in the PC period, unless otherwise defined.

For randomized participants not treated with any study drug, baseline is defined as the last nonmissing assessment before or on the day of randomization for all parameters.

For participants who continue in the OLE period, baseline is defined as follows:

- For efficacy evaluation, baseline is the last nonmissing measurement obtained before the first administration of study drug in the PC period, unless otherwise defined.
- For safety evaluation in the OLE period:
  - For participants who cross over from the placebo group or the INCB054707 15 or 45 mg groups to INCB054707 75 mg, baseline is the last nonmissing measurement obtained before the first administration of INCB054707 75 mg in the OLE period.
  - For participants who take INCB054707 75 mg throughout study participation up to Week 52, baseline is the last nonmissing measurement obtained before the first administration of study drug in the PC period.

For participants who continue in the LTE period, baseline is defined as follows:

- For efficacy evaluation, baseline is the last nonmissing measurement obtained before the first administration of study drug in the PC period, unless otherwise defined.
- For safety evaluation in the LTE period, baseline is the last nonmissing measurement obtained before the first administration of INCB054707 in the LTE period.

When scheduled assessments and unscheduled assessments occur on the same day and the time of the assessment or time of first dose is not available, use the following convention to determine baseline:

- If both a scheduled and an unscheduled visit are available on the day of the first dose and the time is missing, use the scheduled assessment as baseline.
- If all scheduled assessments are missing on the day of the first dose and an unscheduled assessment is available, use the unscheduled assessment as baseline.

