5. STUDY POPULATION

The study population will include men and women aged 18 to 75 years who have had a diagnosis of HS (Hurley Stage I, II, or III) for at least 3 months and who have at least a 5 AN count at screening and baseline with inflammatory lesions that affect at least 2 distinct anatomical areas.

Deviations from eligibility criteria are not allowed because they can potentially jeopardize the scientific integrity of the study, regulatory acceptability, and/or participant safety. Therefore, adherence to the criteria as specified in the Protocol is essential. Prospective approval of Protocol deviations to recruitment and enrollment criteria, also known as Protocol waivers or exemptions, are not permitted.

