5.1. Inclusion Criteria

Participants are eligible to be included in the study only if all of the following criteria apply:

- 1. Men and women age 18 to 75 years inclusive at the time of signing the ICF.
- 2. HS disease duration of at least 3 months before screening.
- 3. Diagnosis of HS defined as:
 - a. A total of at least 5 inflammatory lesions (AN) at screening AND baseline AND
 - b. Inflammatory lesions present in at least 2 distinct anatomical areas
- 4. Willingness to avoid pregnancy or fathering children based on the criteria below.
 - a. Male participants with childbearing potential must agree to take appropriate precautions to avoid fathering children (with at least 99% certainty) from screening through 90 days after the last dose of study drug and must refrain from donating sperm during this period. Permitted methods that are at least 99% effective in preventing pregnancy (see Appendix A) should be communicated to the participants and their understanding confirmed.
 - b. Female participants with childbearing potential must have a negative serum pregnancy test at screening and must agree to take appropriate precautions to avoid pregnancy (with at least 99% certainty) from screening through safety follow-up. Permitted methods that are at least 99% effective in preventing pregnancy (see Appendix A) should be communicated to the participants and their understanding confirmed.
 - c. Female participants without childbearing potential (ie, surgically sterile with a hysterectomy and/or bilateral oophorectomy OR postmenopausal, defined as amenorrhea ≥ 12 months prior to screening), confirmed by FSH levels at screening, are eligible.
- 5. Participants agree NOT to use topical antiseptics (see Section 6.6.2) on the areas affected by HS lesions during the placebo-controlled 16-week treatment period.
- 6. For Germany only, participants must have a history of inadequate response or intolerance to an adequate course of oral antibiotics for treatment of HS, as assessed by the investigator through study participant interview and review of medical history.

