8.1.2. Screening Procedures

Screening is the interval between signing the ICF and the day the participant is randomly assigned to study drug (Day 1). Screening assessments for determination of eligibility may be performed over a period lasting up to 30 days. For participants who are randomized in the study, information associated with eligibility requirements must be entered into the appropriate eCRF pages.

Results from the screening visit evaluations will be reviewed to confirm eligibility before randomization or the administration of study drug. Tests with results that fail eligibility requirements may be repeated once during screening if the investigator believes the results to be in error. For screening assessments that are repeated, the most recent available result before randomization will be used to determine eligibility.

See Sections 5.4 and 5.5 for information regarding screen failures and replacement of participants, respectively.

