8.2. Efficacy Assessments

Efficacy assessments, are provided in this section. Unless an exception is required, the same investigator/designee should perform the efficacy assessments for a participant at each of the participant's efficacy evaluation visits.

The lesion count worksheet (provided in the Study Manual) will be used for recording the abscess, nodule (inflammatory and noninflammatory), fistula (draining and nondraining), and hypertrophic scar counts, and the assessment of Hurley stage. The lesion counts will be used for calculation (by Incyte or designee) of efficacy parameters, including HiSCR and IHS4. Additionally, the number and type of lesional interventions will be documented on this worksheet.

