8.2.1.1. AN and ANF Counts

The AN and ANF counts will be recorded at all visits. The AN results will be used to calculate change in AN count relative to baseline, as well as AN50, AN75, AN90, and AN100, defined respectively as at least a 50%, 75%, 90%, and 100% decrease in AN count relative to baseline. The ANF results will be used to calculate the change in ANF count relative to baseline. Further information will be provided in the Study Manual.

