## 7.1. General Considerations

For participants who enter the OLE period and do not continue in the LTE period, all by-visit analyses for open-label evaluable population will include the follow-up period if the data are available, unless otherwise specified.

For participants who continue into the LTE period, all by-visit analyses for long-term evaluable population will include the follow-up period if the data are available, unless otherwise specified.

Unless otherwise stated, the strata identified in the randomization process will be used in all efficacy analyses.

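### If SAP 7.4.1 does not already include it, add the screening AN count as a prespecified covariate in the Week 16 AN model; the gain is modest and may be zero

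*SAP*

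**What the plan says.** Two pre-dose AN counts exist by design. Inclusion criterion 3a (Protocol 5.1) requires "A total of at least 5 inflammatory lesions (AN) at screening AND baseline". Protocol 5 rules out waivers: "Deviations from eligibility criteria are not allowed because they can potentially jeopardize the scientific integrity of the study". Protocol 8.2.1.1 adds "The AN and ANF counts will be recorded at all visits", and the lesion-count row of the schedule of activities (Table 3) is marked at both screening and baseline.

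The two counts are close together and comparable. Protocol 8.1.2 states "Screening assessments for determination of eligibility may be performed over a period lasting up to 30 days", and Protocol 8.2 asks that, barring exceptions, "the same investigator/designee should perform the efficacy assessments for a participant at each of the participant's efficacy evaluation visits".

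For analysis, SAP 4.1.3 says "Baseline is the last nonmissing measurement obtained before the first administration of INCB054707 or placebo in the PC period", followed by a clause allowing other definitions. In the ordinary case this is the Day 1 count. Change in AN (SAP 7.2.1) and HiSCR (SAP 7.2.2) are both measured from baseline. SAP 4.1.4 refers to MMRM for continuous endpoints with missing values. The only adjustment that can be read is in SAP 7.1: unless stated otherwise, "the strata identified in the randomization process will be used in all efficacy analyses". Those strata are region and Hurley stage (SAP 3.1).

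The text that would list the model covariates (SAP 7.4.1, most of SAP 7.5.1, Protocol 10.4.1) is not readable in the public version.

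**The concern.** One AN count is a noisy reading of a fluctuating disease. If a single pre-dose count only partly captures a participant's usual lesion load, a second count made within the preceding 30 days carries extra information about Week 16. Leaving it out of a linear model would leave some explainable variance in the residual.

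The stake is precision only. Arms have about 50 participants (SAP 3.1), and Protocol 2.1.2 expects the result to drive the choice of one regimen for Phase 3. A free gain is therefore worth a line in the SAP.

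**Working it through.** There is no plan figure to reproduce: the sample-size and alpha text (Protocol 10.1 and 10.3) is not readable, and no AN variance or correlation is given. All correlations below are assumptions, and the Day 1 count is assumed to be in the model already.

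**Formula.** Let S, B and W be the screening, Day 1 and Week 16 AN counts. With B in the model, change from B and W itself have the same residual variance. Adding S multiplies that variance by

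ratio = 1 − (r_SW − r_SB·r_BW)² / [(1 − r_SB²)(1 − r_BW²)].

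With equal correlation r this becomes (1 + 2r)/(1 + r)².

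**Equal correlation**

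| r | Ratio | Variance fall | Equivalent extra participants on 200 (200/ratio − 200) |
|---|---|---|---|
| 0.3 | 1.6/1.69 = 0.947 | 5% | 11 |
| 0.5 | 2.0/2.25 = 0.889 | 11% | 25 |
| 0.7 | 2.4/2.89 = 0.830 | 17% | 41 |

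**Correlation decaying with time.** Take r = a + b·φ^weeks, with screening 3 weeks before Day 1. For (a, b, φ) = (0.4, 0.2, 0.9):

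- r_SB = 0.4 + 0.2 × 0.729 = 0.546
- r_BW = 0.4 + 0.2 × 0.185 = 0.437
- r_SW = 0.4 + 0.2 × 0.135 = 0.427
- fall = (0.427 − 0.546 × 0.437)² / (0.702 × 0.809) = 0.0355/0.568 = 6.3%

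Other settings give 3.8% (0.3, 0.3, 0.9), 7.9% (0.5, 0.2, 0.85), 2.0% (0.2, 0.4, 0.9) and 3.7% (0.2, 0.3, 0.95). In all five settings a + b lies between 0.5 and 0.7, so 30% to 50% of the variance is taken to be pure visit noise. With only 10% noise, (0.3, 0.6, 0.9), the correlations are 0.737, 0.411 and 0.381 and the fall is 0.00606/0.379 = 1.6%. If correlation decays as a Markov chain (r_SB 0.7, r_BW 0.5, r_SW 0.35), the numerator is 0.35 − 0.7 × 0.5 = 0 and there is no gain.

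**Simulation with the entry rule.** Overdispersed Poisson counts, AN of at least 5 forced at both pre-dose visits, 50 per arm, ANCOVA without strata, 600 runs per scenario:

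| r_SB / r_BW / r_SW (placebo) | AN variance ratio | AN power without → with S |
|---|---|---|
| 0.61 / 0.54 / 0.53 | 0.916 | 98.5% → 98.7% |
| 0.59 / 0.50 / 0.50 | 0.919 | 90.0% → 91.0% |
| 0.42 / 0.31 / 0.31 | 0.961 | 79.0% → 80.5% |
| 0.30 / 0.23 / 0.22 | 0.977 | 80.7% → 81.7% |

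**Power.** Assume two-sided alpha 0.05 and an effect of 0.560 residual SD, which gives 80% power at 50 per arm with B alone. Power is then Φ[0.560/(0.2·√ratio) − 1.96]. A ratio of 0.98 gives 81%, 0.92 gives 83% and 0.889 gives 84%.

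**HiSCR.** In the same simulation, logistic regression on a response of at least 50% AN reduction had power 92.5% → 93.0%, 79.8% → 83.0%, 68.3% → 69.5% and 67.0% → 68.0% when S was added to B, in the same row order. These gains of about 0.5 to 3 points are mostly within simulation error.

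**The case against.** Four inferences are tempting, and the objections to them are sound.

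- *That the SAP leaves the screening count out of its models.* The documents do not show this. SAP 4.1.3 defines the reference value for change; it neither lists nor excludes covariates, and it allows exceptions. SAP 7.4.1 cannot be read, and text withheld from the public version is not missing from the plan. Even the Day 1 count as a covariate is not visible.
- *That HiSCR gains in the same way.* Its model cannot be read. Both documents cite a reference on exact logistic regression. In a logistic model, adjustment does not shrink the standard error as it does in a linear one, and it changes the odds ratio being estimated. If an exact method is planned, a second continuous covariate may be hard to carry. The HiSCR reference also stays the single baseline, so a covariate cannot undo misclassification from a noisy Day 1 count.
- *That the gain is 14% to 17%.* That needs equal correlations of 0.6 to 0.7 across a gap of at most 30 days and a 16-week gap that includes treatment. The strata already absorb some variance: if they explained 20% at each visit (an assumption), r = 0.5 becomes (0.5 − 0.2)/0.8 = 0.375, and the fall drops from 11% to 1 − 1.75/1.375² = 7%. The entry rule truncates both pre-dose counts and lowers their correlation further.
- *That the screening count is always single and complete.* Protocol 5.4 and 8.1.2 allow repeats and rescreening, and Protocol 7.1.1 provides for participants later found ineligible, who stay in the ITT population. Without a rule, a missing covariate could drop them from the model.

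Using the last pre-dose value as baseline is conventional and unbiased; no error, contradiction or type I error problem is shown. What survives is an optional efficiency gain in the AN model.

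**Conclusion.** The point holds as a minor, conditional suggestion for the AN model. Two pre-dose counts exist by design, and the readable SAP makes efficacy use of only one. Adjusting a linear model for a pre-randomisation count leaves the estimand unchanged and, in large samples, cannot raise the residual variance.

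The plausible fall is roughly 2% to 8%, equivalent to about 1 to 4 participants per arm (50/0.98 = 51.0; 50/0.92 = 54.3). It reaches about 11% with equal correlation 0.5, and is zero if the screening count adds nothing once the Day 1 count is known. The size rests wholly on assumed correlations and on the Day 1 count being in the model. Whether any change is needed depends on SAP 7.4.1.

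**What to change.** Check the covariate list in SAP 7.4.1. If the screening AN count is there, stop. If not, before the primary database lock and unblinding:

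- Add the screening AN count as a prespecified covariate in the MMRM for change in AN count, next to the Day 1 AN count and the randomisation strata.
- Keep the Day 1 count as the reference for change, AN50 to AN100 and HiSCR.
- State that, after a repeat or rescreening, the most recent screening count before Day 1 is used. Rescreened participants receive a new number (Protocol 5.4), so say which record supplies it.
- State that a missing screening count is imputed from pre-randomisation data, for example the Day 1 count, so that no ITT participant is dropped.
- Treat its use in the HiSCR model as optional, with no precision gain claimed.

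The cost is a few lines of SAP text and one parameter, or about six if the covariate is interacted with the six post-baseline visits (Weeks 2, 4, 6, 8, 12 and 16). No new data are needed.
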